9.6 DATA MANAGEMENT

A data validation plan (DVP) and a data management plan (DMP) will be created to describe all functions, processes, and specifications for data collection via the electronic Case Report Forms (eCRFs). The eCRF will include programmable edits to obtain immediate feedback if data are missing (also negative answers, unknown), out of range, illogical or potentially erroneous. These rules may encompass simple checks such as range validation or presence/absence of data. Concurrent manual data review including query processes may be performed as defined in the data management plan (DMP). This involves ad hoc queries within the eCRF which will be followed up for resolution. The database will be hosted in a physically and logically secure computer system maintained in accordance with a written security policy. The system will meet the standards of the International Committee on Harmonization guideline E6R1 regarding electronic study data handling. Data confidentiality will be strictly maintained.

9.7 DATA ANALYSIS

Details will be described in the statistical epidemiological analysis plan (SEAP)

9.7.1 Planned analyses

All patients who have received a first prescription of respective study medication will be included in the analysis; this is the prescribed patient set. All analyses will be performed on the prescribed patient set. If patients have missing values for an outcome, those patients will be excluded for that outcome's analysis.

The assessment will be carried out using SAS® software. The statistical characteristics presented in the end-of-text tables will be N / mean / SD / min / median / max for continuous variables. Tabulations of relative and absolute frequencies will be presented for categorical variables. Incidence rates and 95% CI will be given when appropriate. Subgroup analyses e.g. according to medication (i.e. empagliflozin or SGTL2i or DPP4i or GLP1a), country and physician specialty are planned, as well as per history of CV disease. Descriptive analyses will be supplemented using χ^2 -test or Fisher's exact test for categorical variables and Wilcoxon-Mann-Whitney test for continuous variables. The analyses are purely explorative, hence no correction for multiple testing is needed.

[figure not shown]
The analyses will relate to the following data as recorded in the eCRF:

1. Patient demographics (age, gender, height, weight, BMI, ethnicity)
2. Time since diagnosis of Type 2 Diabetes
3. Clinical parameters relevant for T2D, CVD, CKD assessment as valid on index date 1
4. Comorbidities like cardiovascular disease and related risk factors at index date 1
5. Comorbidities like chronic kidney disease and related risk factors at index date 1
6. T2D medication the treating physician newly prescribes at study index date 1
7. Reason(s) for treatment decision at index date 1
8. Concomitant T2D medications at study index date 1
9. Concomitant CVD and CKD medications at index date 1
10. Other HCPs involved in treatment decisions at study index date 1 and at index date 2
11. Relevant socioeconomic parameters
12. Discontinuation rate, reason for discontinuation, duration of T2D therapy after one year (± 2 months)

All adverse events and adverse drug reactions collected per study protocol will be included and summarized in the final study report. Refer to the corresponding [Section 11](#).

Main analysis

For the main analysis data from research question 1 to 5 will be evaluated in a descriptive manner for the total number of prescribed patients enrolled in the study.

9.7.2 Handling of missing data

By using a simple and non-complex eCRF in which the amount of data to be assessed is limited, the amount of missing data is expected to be low. Every effort will be made to collect complete data by using validation checks within the eCRF and possibly involving manual query processes (see Section 9.8). Please refer to the analysis plan for details.

9.8 QUALITY CONTROL

The study sites will be trained on the study procedures and on handling of the eCRF before documentation of the first patient at the respective study site.

To ensure data quality, automatic data checks upon data entry (eChecks) will be programmed within the eCRF. Therefore, plausible ranges of values for numeric data entries as well as logical data entries and listings will be provided for the respective entry field. Based on this, checks on completeness and plausibility will be performed upon data entry in the eCRF.

Validity of data entry thus is ensured by integrated validation checks performed by the system, indicating missing or implausible entries to the document list or investigator. All corrections will be visible from the systems audit trail. Data management activities by means of manual query processes might be implemented as defined in the DMP to increase data integrity.

No regular source data verification is planned in this study. However, in case of decreasing data quality (i.e. of missing data, data discrepancies, protocol violations, etc.) a for-cause audit or risk-based monitoring visit will be performed.

9.9 LIMITATIONS OF THE RESEARCH METHODS

The intention of this NIS is to analyze existing data of T2D patients when initiating on different types of T2D drugs, their comorbidities, their co-medications and socioeconomic factors with possible influence on treatment decisions and treatment duration.

A NIS is the most suitable instrument for obtaining information about the use of medicines in everyday clinical practice.

A possible limitation of the retrospective study design of this NIS is that the time windows of 4 months (index date 1) and of 12 (\pm 2) months (index date 2) will give limited information in the population at a specific point in time. Medication availability might differ between countries due to different reasons (commercial availability, reimbursement status) which will be collected in research question 4 for further data interpretation.

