8.2 STUDY OBJECTIVES

The objective of the study is

1. To describe and compare T2D patients' baseline characteristics when initiating either empagliflozin - or other SGLT2i, DPP4i or GLP1a on top of current antidiabetic treatment by different HCP specialties in CEE countries
2. To describe the prevalence of comorbidities (prevalence of CVD, CKD) in this T2D patient population at index date 1
3. To describe and compare the actual treatment uses at index date 1 in patients with and without established CVD

Established CV disease defined as acute myocardial infarction (AMI), cardiology intervention, ischemic heart disease (IHD), congestive heart failure (CHF), peripheral arterial disease (PAD), or stroke.

4. To describe the association of socioeconomic parameters with treatment decisions at index date 1
5. To assess the discontinuation rate, reasons for discontinuation and average duration of treatment for GLP1a, DPP4i and SGLT2i after a follow up of approximately one year from the initial timepoint (= index date 2)

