 - sitagliptin
 - saxagliptin
 - vildagliptin
- GLP1a
 - dulaglutide
 - exenatide
 - liraglutide
 - semaglutide
 - lixisenatide
- Reasons for choosing the treatment rated as not relevant at all/ moderately relevant/ highly relevant
 - HbA1c lowering
 - Weight loss

- Cardiovascular risk reduction
- Favorable side effect profile
- Simple dosing / administration
- Guideline recommendation

[figure not shown]
6. Concomitant T2D medications (given as monotherapy or as fix combination with main T2D medication) at study index date 1
 - Metformin
 - Sulfonylurea
 - Acarbose
 - Pioglitazone
 - Insulin
 - others
7. Concomitant CVD and CKD medications at index date 1 (on class level only)
 - Antihypertensives ACEi or ARBs
 - Statins
 - Low dose aspirin
 - Beta blockers
 - Diuretics
8. Involvement of other HCPs in treatment decisions with regard to SGLT2i, DPP4i or GLP1a prescription at study index date 1 and with regard to discontinuation at index date 2 (yes/no; if yes, the medical specialty of the involved physician(s) should be specified)
9. Association of socioeconomic parameters with treatment decisions (such as employment status, family status, type of health insurance) at study index date 1
10. Status of T2D therapy approximately one year (\pm 2 months) after start
 - Stop date, if available
 - Reasons for discontinuation
 - Investigator's decision
 - Patient's request (difficulties in medication handling)
 - Patient's request (financial burden regarding co-payment)
 - Patient's request (other)
 - Lost to follow-up
 - Adverse event (in case of adverse reaction to empagliflozin or linagliptin or fatal adverse event, see [Section 11](#))
 - Death
 - Unknown
 - Other

Primary outcomes

- T2D patients' baseline characteristics when initiating either empagliflozin - or other SGLT2i, DPP4i or GLP1a on top of current antidiabetic treatment by different HCP specialties in CEE countries.

Secondary outcomes

- Burden of comorbidities (prevalence of CVD, CKD and CVD/CKD risk factors) in this T2D patient population at study index date 1
- Actual treatment use at study index date 1 in patients with and without established CVD (Established CV disease defined as acute myocardial infarction (AMI), cardiology intervention, ischemic heart disease (IHD), congestive heart failure (CHF), peripheral arterial disease (PAD), or stroke)
- To describe the association of socioeconomic parameters with treatment decisions at study index date 1

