9.12 BIAS

Selection bias could occur at the site level and the patient level.

To minimize the site level selection bias, sites will be eligible if HCPs initiate second line medications in their T2D patients. In addition to that, the number of proposed sites will be 150% of sites to be finally included which will allow random selection of site.

In order to limit the variability of outcomes, sites will be eligible if they have access and can prescribe at least 2 of the T2D drug classes of interest (SGLT2i, DPP4i, GLP1a) for the targeted T2D.

To minimize selection bias at the patient level, physicians are requested to include all patients meeting inclusion and exclusion criteria in the study period of 4 months (September – December 2018) into the study. However, there may be a bias regarding patient groups at index date 1 and 2, since not all patients who have consented to documentation at index date 1 may or can give their consent (e.g. due to death or loss to follow-up) to further documentation at index date 2.

Information bias will be minimized by the use of standard eCRF and physicians' training on the study protocol and handling of the eCRF.

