7.3 PRIMARY OUTCOME

For the primary outcome, the baseline characteristics will be analysed in a descriptive manner. Frequencies and 95% CI will be given when appropriate.

In addition the baseline characteristics will be compared by medication, physician speciality and country using χ^2 -Test or Fisher's exact test, if χ^2 -Test is not valid, for categorical variables and Wilcoxon-Mann-Whitney test for continuous variables.

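### Protocol 9.9 promises availability and reimbursement data that no listed variable records, so access limits can pass for patient selection in the pooled comparisons by medication

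*Protocol*

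**What the plan says.** Protocol 9.9 names unequal drug availability as a limitation and gives this answer: "Medication availability might differ between countries due to different reasons (commercial availability, reimbursement status) which will be collected in research question 4". Research question 4 in Protocol 8.2 reads: "To describe the association of socioeconomic parameters with treatment decisions at index date 1". Section 9.3.2 names its variables as "such as employment status, family status, type of health insurance".

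Also in 9.3.2, the prescriber scores "Reasons for choosing the treatment rated as not relevant at all/ moderately relevant/ highly relevant". The six visible items concern glucose, weight, cardiovascular risk, tolerability, ease of use and guidelines. The only cost item in the variable list is "Patient's request (financial burden regarding co-payment", which is a reason for stopping, recorded at index date 2.

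On site selection, Protocol 9.12 states that "sites will be eligible if they have access and can prescribe at least 2 of the T2D drug classes of interest", and 9.2 sets the same rule. The listed site data are the physician's age and gender and the practice's postal code (9.2).

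On analysis, SAP 7.3 states that "the baseline characteristics will be compared by medication, physician speciality and country". SAP 7.4 uses the χ²-test or Fisher's exact test to examine whether treatment decisions depend on socioeconomic factors. Covariates (Protocol 9.3.3) and pooling of centres (SAP 6.5) are both marked not applicable. SAP 7 also plans a descriptive evaluation of research questions 1 to 5 for each country.

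**The concern.** The protocol recognises that availability may differ and then relies on data that its own lists do not contain. At a site without a given class, no patient can receive that class, whatever the prescriber would have chosen. Those patients still enter the all-site comparison by medication. If they differ in cardiovascular history, age or income from patients at sites with full access, the drug groups will differ even when choice within each site is unrelated to those characteristics.

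Two results are exposed: the primary comparison of who starts which drug, and objective 4 on socioeconomic factors and choice. The protocol's rationale (8.1) stresses limited healthcare spending in the region and factors that may restrict use of these drugs, so readers will want to know whether a difference reflects choice or access.

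**Working it through.** **1. The promise set against the lists.**

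| Place | What is listed | Availability, reimbursement or site classes? |
|---|---|---|
| Protocol 9.3 and 9.3.2 | "Association of socioeconomic parameters with treatment decisions (such as employment status, family status, type of health insurance) at study index date 1" | Not named; insurance type is a partial patient-level proxy |
| Protocol 9.3.2, reasons for choice | Six items, none on cost or access | Not named |
| Protocol 9.3.2, reasons for stopping | Co-payment burden | Only at index date 2, only on stopping |
| Protocol 9.7.1 and 9.10.2.2.1; SAP 7 | Relevant socioeconomic parameters, reasons for decision | Not named |
| Protocol 9.2, site data | Physician age and gender, postal code | Not named; access is an eligibility check only |

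No listed variable matches the statement in 9.9.

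**2. Plan figures.** The study size of about 4000 has no formal calculation behind it (Protocol 9.5), so there is no figure to reproduce. The subgroup aspirations are 500 GLP1a, 1000 SGLT2i and 1000 DPP4i. They sum to 2500, which is compatible with 4000.

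**3. How large could the effect be?** This is an illustration.

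Inputs from the documents: 4000 patients; 500 on GLP1a; 34% CVD prevalence (the Swedish figure cited in Protocol 8.1), used here for full-access sites.

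Assumptions: the other 3500 patients split equally, so 1750 are on DPP4i; drug choice is unrelated to CVD within every site; a share s of all patients is at sites without GLP1a; CVD prevalence there is d points lower; no clustering by site.

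All GLP1a patients come from full-access sites, so their prevalence is 34%. The share of DPP4i patients at sites without GLP1a is

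w = (4000·s/2) / 1750

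and the spurious gap is w·d. For s = 50% and d = 10 points: w = 1000/1750 = 0.571, DPP4i prevalence = 34 − 5.7 = 28.3%, gap = 5.7 points.

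The chance of p<0.05 in the direction of the gap (two-sided 5% test, normal approximation) is Φ((gap − 1.96·SE0)/SE1), where SE0 is the pooled and SE1 the unpooled standard error. In the same case SE0 = 0.0231 and SE1 = 0.0238, so Φ((0.0571 − 1.96·0.0231)/0.0238) gives 69%.

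| s | w | gap for d = 5 / 10 / 15 points | chance of p<0.05 |
|---|---|---|---|
| 10% | 0.114 | 0.6 / 1.1 / 1.7 | 4% / 7% / 11% |
| 25% | 0.286 | 1.4 / 2.9 / 4.3 | 9% / 23% / 45% |
| 50% | 0.571 | 2.9 / 5.7 / 8.6 | 23% / 69% / 96% |

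Limited to sites able to prescribe both classes, the gap is 0 by construction. The documents give neither s nor d.

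**The case against.** Several points on the other side have force.

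- **The list is open.** The socioeconomic parameters are introduced as examples, and the eCRF forms cited in Annex 1 are not among the documents. A reader might infer that the data will certainly be absent. The documents support only that no *listed* variable matches.
- **Per-country results are planned.** The statement in 9.9 concerns differences between countries, and SAP 7 evaluates every research question by country. This partly meets the problem that 9.9 raises. It is descriptive, does not separate sites within a country, and leaves the pooled tests in SAP 7.3 and 7.4 unchanged.
- **The effect is conditional.** A reader might infer that access limits will distort the comparison. That needs both a material share of patients at sites lacking a class and a different patient mix there. Nothing shows how many sites, if any, lack a class, and at s = 10% the gap is small.
- **The study is descriptive.** In drug-utilisation research, limited access is part of the real-world pattern, and the protocol does not claim to isolate prescriber preference. This lowers the stakes. It does not excuse citing interpretive data that the lists omit.
- **Feasibility answers may not be usable.** Protocol 9.2 describes an eligibility check. It does not say that answers were stored per class, and it describes no reimbursement question.

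**Conclusion.** The point holds as an inconsistency with a conditional consequence. The remedy in 9.9 has no counterpart in the listed variables, so the planned data, as listed, cannot show whether a difference between drug groups reflects choice or access. Insurance type is only a partial proxy, and co-payment is recorded only at stopping.

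Under the stated assumptions, the spurious GLP1a versus DPP4i gap in CVD prevalence runs from about 0.6 to 8.6 points: negligible at one end and likely to reach p<0.05 at the other. The documents do not show where in that range the study lies, and they do not support saying that the bias is certain or large. For an exploratory study this should be corrected, but it does not invalidate the design.

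**What to change.** 1. Record for each site which of the three classes it could prescribe in September to December 2018, by a short query where feasibility did not store the answer. Record reimbursement status per drug and country for the same period. Carry both into the analysis dataset.
2. Add to SAP 7.3 a supplementary table for each pair of classes, limited to sites able to prescribe both, beside the planned all-site table.
3. Where charts allow, add one item to the reasons for choice covering cost, reimbursement and availability.
4. If these data are not collected, delete the statement in Protocol 9.9 and say that the comparisons by medication and the socioeconomic analysis do not separate choice from access. If the eCRF already holds such an item, name it in 9.3.2 and SAP 7.

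Cost: a short site query, a possible return to the charts for patients already documented (item 3 only), and fewer patients in the restricted tables. Items 1 and 2 need no contact with patients.

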9.10 OTHER ASPECTS

9.10.1 Informed Consent, Data Protection, Study Records

The study will be carried out in compliance with the protocol, the principles laid down in the Declaration of Helsinki, and as close as possible to the standards of the International Conference of Harmonisation (ICH) Tripartite Guideline for Good Clinical Practice (GCP), Guidelines for Good Epidemiological Practice (GEP) [R10-4560], Good Pharmacoepidemiology Practice (GPP) [R09-0182] and relevant BI Standard Operating Procedures (SOPs).

The rights of the investigator and of the sponsor with regard to publication of the results of this study are described in the investigator contract. As a general rule, no study results should be published prior to finalization of the Study Report.

9.10.2 Study Approval, Patient Information, and Informed Consent

This study will be initiated only after all required legal documentation has been reviewed and approved by the respective Independent Ethics Committee (IEC) and competent authority (CA), if needed according to national and international regulations. The same applies for the implementation of changes introduced by amendments.

Patients potentially eligible for study participation will be contacted by the delegated site personnel by phone or by sending a letter, reminding the patient of the next routine visit. In addition, patients will be informed about the study project and his/her potential eligibility for participating in the study.

Prior to patient participation in the study, written informed consent must be obtained from each patient (or the patient's legally accepted representative). Each signature must be personally dated by each signatory and the informed consent and any additional patient-information form retained by the investigator as part of the study records. A signed copy of the informed consent and any additional patient information must be given to each patient or the patient's legally accepted representative.

The patient must be informed that his/her personal study-related data will be used by Boehringer Ingelheim in accordance with the local data protection law. The level of disclosure must also be explained to the patient.

The patient must be informed that his / her medical records may be examined by authorized monitors (CML/CRA) or Clinical Quality Assurance auditors appointed by Boehringer Ingelheim, by appropriate IEC members, and by inspectors from regulatory authorities.

After having provided written informed consent, the patients will be registered within the study's EDC system to document all relevant variables.

Patients already registered before protocol amendment 1 will have to consent to additional data collection at index date 2.

9.10.2.1 Data Quality Assurance

A quality assurance audit/inspection of this study may be conducted by the sponsor or sponsor's designees or by IECs or by regulatory authorities. The quality assurance auditor will have access to all medical records, the investigator's study-related files and correspondence, and the informed consent documentation of this study.

9.10.2.2 Records

All of the clinical data and site/investigator characteristics will be captured via a web-based Electronic Data Capturing system. The delegated site staff will enter and edit the data via a secure network, with secure access features (username, password and secure identification – an electronic password system). A complete electronic audit trail will be maintained.

Patients must not be identified on the eCRF by name. Appropriately coded identification (i.e. Patient numbers) must be used.

9.10.2.2.1 Source documents

The relevant study data will be derived from the patient's medical record, which is maintained either paper-based or electronically depending on the routine at the respective study site. Data relevant for this study will be reviewed and entered into the study's eCRF by delegated site staff. Data entered in the eCRFs that are transcribed from source documents must be consistent with the source documents.

Source documents provide evidence for the existence of the patient and substantiate the integrity of the data collected.

For the eCRF, the following data must be derived from source documents:

1. Patient demographics (age, gender, height, weight, BMI, ethnicity)
2. Time since diagnosis of Type 2 Diabetes
3. Clinical parameters relevant for T2D, CVD, CKD assessment as valid on index date 1
4. Comorbidities like cardiovascular disease and related risk factors at index date 1
5. Comorbidities like chronic kidney disease and related risk factors at index date 1
6. T2D medication the treating physician newly prescribes at study index date 1
7. Reason(s) for treatment decision at index date 1
8. Concomitant T2D medications at study index date 1
9. Concomitant CVD and CKD medications at index date 1
10. Other HCPs involved in treatment decisions at study index date 1 and at index date 2
11. Relevant socioeconomic parameters
12. Status of T2D treatment (stop date and reason for discontinuation, if available) at index date 2

